Official title: Early Childhood Outside (ECO) Early Childhood Educator (ECE) Tool -
Randomized Controlled Trial Study

NCT number: NCT04624932

Document date: July 28, 2022

Document type: Study Protocol with
Statistical Analysis Plan

Study Protocol

Objectives

Our study objective is to develop and evaluate a web-based intervention that influences early childhood educators' (ECEs) and early learning child care (ELCC) administrators' perceptions and practices in support of children's outdoor play in ELCCs.

Design

This study is guided by the 6-step Intervention Mapping process (Michie et al., 2008) to plan, develop and evaluate the web-based intervention as described in Objectives. Upon receiving ethics approval from the University of British Columbia and Children's and Women's Health Centre of British Columbia Research Ethics Board (H19-01230; H19-03644), we began with Step 1 to understand the problem. This was done by establishing and working with study partners from various disciplines; and, conducting a literature review and a need assessment of the target population through focus groups – to explore key issues, needs and challenges from different perspectives. A logic model of the problem was developed to establish intervention goals. Step 2 involved developing a logic model of change to identify what needs to change and for whom. This linked the behavioral and environmental change objectives to specific outcomes that helped meet the intervention objectives. Then we selected the optimal applications and technology to deliver the intervention (Step 3) to produce the intervention (Step 4). In Step 5, we developed the intervention implementation and mobilization plan to make sure this web-based intervention reaches the target audiences. For the final step (Step 6), we will conduct a single-blind randomized control trial to test the efficacy of the web-based intervention.

Methods

We used a single-blind (researchers and outcome assessors), two-parallel-group randomized controlled trial design to evaluate the efficacy of the intervention. Consenting, randomization, survey administration and follow-ups was managed strictly online. We recruited 563 ECEs and ELCC administrators at baseline through a variety of online means, including Facebooks Ads and mass emails through our partner networks. Participants were randomized into the intervention or the control group by the REDCap, an electronic data capture intervention, hosted by the BC Children's Hospital Research Institute. Participants had equal likelihood of assignment to each group using a basic randomization method. The control group read Position Statement on Active Outdoor Play, a 4-page document on research and recommendations for action in addressing barriers to outdoor play (Tremblay et al., 2015). The intervention group took the web-based intervention to influence ECEs and ELCC administrators' perceptions and practices in support of children's outdoor play in ELCCs.

The primary outcome is increased tolerance of risk in children's play, as measured by the Teacher Tolerance of Risk in Play Scale. The secondary outcome is self-reported attainment of a self-developed behavior change goal at either two follow-up time point.

For complete study protocol, refer to: Brussoni M, Han CS, Jacob J, Munday F, Zeni M, Walters M, Cheng T, Schneeberg A, Fox E, Oberle E. A web-based risk-reframing intervention to influence early childhood educators' attitudes and supportive behaviors toward outdoor play: Protocol for the outsideplay study randomized controlled trial. *JMIR Research Protocols*; 2021;10(11):e31041. [doi: 10.2196/31041]

Statistical Analysis Plan

Statistical software

The latest version of R (R Foundation for Statistical Computing, Vienna, Austria) and Stata (StataCorp LLC, College Station, TX, USA) was used for statistical analysis and graphics.

Power

For a sample size of 206 ECEs and ELCC administrators in total, a linear mixed model examining the impact of intervention relative to control, including an interaction with time, was calculated to have 80% power at a $P=.05$ level of significance to detect a difference of 0.75 between the intervention and control conditions on the T-TRiPS when the SD is 1.82, and the correlation between repeated observations is 0.75. From our previous work (Brussoni et al., 2021), we anticipated requiring 324 complete baseline requirements among ECEs and ELCC administrators who would then be randomized into the 2 conditions. We assumed a 75% retention rate at the 1-week postintervention follow-up time point ($n=242$) and an 85% retention rate at our 3-month postintervention follow-up time point, which would result in a final sample of 206 ECEs, corresponding to 103 in each condition.

Measurement occasions and follow-ups

Participants completed a questionnaire package at three time points: baseline (T1), 1-week post-intervention (T2) and 3-month post-intervention (T3). Long-term change is unlikely if participants do not make initial changes, thus, the 1-week follow-up was selected to assess short-term effectiveness, while still providing participants sufficient time to make their initial planned changes. The 3-month follow-up assessed long-term effectiveness once participants have had several months to reflect on the intervention and implement change. Survey data were collected and managed using REDCap. Baseline data collection includes socio-demographic data: sex, age, ethnicity, spoken language, years working in the early learning childcare field, years working in the current ELCC center, role in the current ELCC center, province of employment, whether the center is licensed, number of children at the center, number of staffs at the center, whether the center has a designated outdoor space for children, quality of the center's outdoor space for children, hours children spent playing outdoors at the center, and whether the participant feels supported by colleagues in general.

We assessed the primary outcome measure at baseline, 1-week, and 3-month post-intervention. We could only assess the secondary outcome measure at 1-week and 3-month post-intervention because at baseline participants could not have accomplished a goal they had not yet set.

Outcome measures

Our primary outcome measure is change in the total score on the Teacher Tolerance of Risk in Play Scale (T-TRiPS), a validated, reliable 26-item measure with dichotomous yes/no responses on items that reflect Sandseter's (Sandseter, 2009) six categories of risky play (great heights, high speed, dangerous tools, dangerous elements, rough-and-tumble, disappear/get lost) (Ihrig, 2020). The T-TRiPS is a modified version of the TRiPS for parents (Hill & Bundy, 2014) measuring teachers' perception of risk. We assessed the psychometric properties of T-TRiPs in our sample using Rasch analysis, using mirt package in R software (Chalmers, 2012). Items with local dependence will be dropped and model fit amongst the remaining items will be assessed: root mean square error of approximation, standardized root mean square residual, Tucker–Lewis index, comparative fit index, and empirical reliability. Theta standardized scores will be obtained for the analysis and a higher standardized score indicates higher tolerance of risk in play.

Our secondary outcome measure is self-reported behavior change, measured by participants' self-reported progress on attaining the goal they set for themselves. At each follow-up time point,

participants will be reminded of their goal and asked “Did you accomplish your goal?” with dichotomous yes/no responses.

Descriptive Analysis

To compare the raw outcome differences between conditions at each time point, for continuous outcomes (TRiPS scores), we used 1-way ANOVA or Kruskal-Wallis H test (if variance is not equal between conditions). For categorical outcomes (goal attainment), we used the chi-square test. Significance level was set at $P=.05$.

For complete results, refer to: Brussoni M, Han CS, Lin, Y, Jacob J, Munday, F, Zeni M, Walters M, Oberle E. Evaluation of the Web-Based OutsidePlay-ECE Intervention to Influence Early Childhood Educators' Attitudes and Supportive Behaviors Toward Outdoor Play: Randomized Controlled Trial. *JMIR*; 2022; 24(6):e36826. [doi: 10.2196/36826]

References

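### No analysis described in the plan is stated to adjust for the pre-randomisation T-TRiPS score; if change scores or free baseline means are used, precision is lost (12.5% of the variance for one follow-up at the plan's correlation)

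*Combined protocol and SAP*

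**What the plan says.** Under Outcome measures, the SAP states: "Our primary outcome measure is change in the total score on the Teacher Tolerance of Risk in Play Scale (T-TRiPS". The same paragraph says that standardised Rasch theta scores will be analysed.

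Under Power, the calculation is for "a linear mixed model examining the impact of intervention relative to control, including an interaction with time". The arm difference to be detected is 0.75 points, "when the SD is 1.82, and the correlation between repeated observations is 0.75". No fixed effects or covariates are listed.

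Under Measurement occasions and follow-ups, T-TRiPS is collected at baseline (T1), 1 week (T2) and 3 months (T3). The Power section has completed baselines preceding randomisation, and Methods describes simple 1:1 allocation with no stratification mentioned.

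The only between-arm comparison written out is under Descriptive Analysis. Its purpose is "To compare the raw outcome differences between conditions at each time point", by one-way ANOVA or Kruskal-Wallis. T1 is one of the three named time points, so this wording takes in a test at baseline.

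No baseline T-TRiPS covariate, ANCOVA or common-baseline constraint appears in the document. It refers to a separate publication for the complete protocol.

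**The concern.** At a correlation of 0.75, the baseline score should predict the follow-up score well. A change score uses it, but fixes its coefficient at 1, whereas with equal SDs the best coefficient is the correlation. A mixed model with an arm-by-time interaction and separate baseline means per arm does the same. Because T1 precedes randomisation, the arms have equal expected baseline means, so baseline adjustment estimates the same arm difference with smaller variance whenever the correlation is below 1.

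What is at stake is the width of the primary confidence interval. The document does not let a reader tell whether the efficient or the less efficient version was meant. Separately, a between-arm test at T1 examines a null hypothesis that randomisation makes true, so it informs nothing.

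**Working it through.** **Inputs from the SAP, Power section:** difference 0.75; SD 1.82; correlation ρ = 0.75; 80% power; 5% significance; 206 in total, 103 per arm; 324 at baseline; 75% retention at T2 and 85% of those at T3. **Assumed here:** two-sided test, the same SD at every visit, one ρ for every pair of visits, normal approximation.

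**1. The plan's own figure.** n per arm = 2 × f × SD² × (1.96 + 0.8416)² / 0.75², where f is the variance factor of the estimator.
- Change score, or interaction with free baseline means, f = 2(1 − ρ) = 0.500: 2 × 0.5 × 3.3124 × 7.849 / 0.5625 = 46.2, so 47 per arm, 94 in total. Power at 103 per arm is 98.7%.
- Baseline-adjusted, f = 1 − ρ² = 0.4375: 40.4, so 41 per arm, 82 in total. Power at 103 per arm is 99.4%.
- Follow-up score alone, f = 1: 92.4, so 93 per arm, 186 in total.

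None of these gives 206. The retention chain does (324 × 0.75 × 0.85 = 206.6). The stated sample size therefore cannot show which model was meant.

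**2. One follow-up, complete data.** SE = 1.82 × √(f × 2/103).
- Change: 1.82 × √(0.500 × 2/103) = 0.179.
- Adjusted: 1.82 × √(0.4375 × 2/103) = 0.168.
- Variance ratio: 0.4375/0.500 = (1 + ρ)/2 = 0.875, a 12.5% reduction. Adjusted, 206 completers carry the information of 206/0.875 ≈ 235.

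**3. Mean of both follow-ups, complete data.**
- Change: (1 + ρ)/2 + 1 − 2ρ = 0.375.
- Adjusted: (1 + ρ)/2 − ρ² = 0.3125.
- Ratio 0.833, a reduction of one sixth.

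**4. The plan's retention.** Of 324 randomised, 25% have T1 only, 11.25% have T1 and T2, and 63.75% have all three. Generalised least-squares variances of the arm difference in change, using all observed data:

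| Setting | Contrast | Free baseline means | Common baseline mean | Reduction |
|---|---|---|---|---|
| 206 complete | T2 or T3 | 0.0322 | 0.0281 | 12.5% |
| 206 complete | mean of T2 and T3 | 0.0241 | 0.0201 | 16.7% |
| 324 with dropout | T2 | 0.0264 | 0.0239 | 9.7% |
| 324 with dropout | T3 | 0.0298 | 0.0273 | 8.6% |
| 324 with dropout | mean of T2 and T3 | 0.0205 | 0.0179 | 12.5% |

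The single-visit gain shrinks because the free-mean model also uses participants with T1 only. Simple change scores in those followed up would still lose 12.5% against ANCOVA in the same people, since n cancels.

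**5. Other correlations.** For one follow-up with complete data the reduction is (1 − ρ)/2: 25% at 0.5, 20% at 0.6, 12.5% at 0.75, 5% at 0.9.

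**6. Chance imbalance.** A one-SE baseline imbalance is 1.82 × √(2/103) = 0.254. The change score then over-corrects by (1 − 0.75) × 0.254 = 0.063. Squared, this is 0.0040, exactly the gap between the two variances in step 2 (0.0322 − 0.0281, before rounding).

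**The case against.** The strongest reply is that the document is silent rather than wrong. Naming change as the outcome defines what is measured, not how it is estimated, and is compatible with ANCOVA. A mixed model of T1 to T3 with arm means constrained equal at T1 also includes an interaction with time, fits the power paragraph's description, and has the ANCOVA variance. The complete protocol lies elsewhere and may name the model. All of this stands: a reader might infer that the plan chose an unadjusted analysis, and the text does not say so.

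The second reply is that little is lost. On the plan's inputs, power at 206 is 98.7% against 99.4%, the SE falls by about 6%, and 563 were recruited against 324 planned. This also stands, and it limits the point to precision.

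Two other inferences are tempting and fail:
- That chance baseline imbalance biases the estimate. Step 6 shows that the shift is the same inefficiency seen another way. Under randomisation each estimator is unbiased on average.
- That adjustment would cut the primary variance by 56% (1 − 0.4375), taking the raw per-visit tests as the primary analysis. The SAP heads those tests as descriptive.

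**Conclusion.** The point holds as a conditional one about precision. The plan is not stated to adjust for baseline T-TRiPS in any analysis it describes. If it uses change scores, or a mixed model with free baseline means, it gives up 12.5% of the variance at one follow-up with complete data. For the mixed model under the plan's retention it gives up about 9-10% at a single visit, and for the mean of both follow-ups 12.5-17%. If the intended model already had a common baseline mean, nothing is lost and saying so closes the point.

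The figures rest on equal variances, a common ρ of 0.75 and randomisation after baseline. The SD and ρ are given for the T-TRiPS, while theta scores are analysed, so the gain on that scale is an assumption, with 5% (ρ = 0.9) to 25% (ρ = 0.5) as a reasonable range.

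**What to change.** Keep the estimand: the arm difference in T-TRiPS change at T2 and at T3. State that it is estimated by one of two models:
- a mixed model of the T2 and T3 scores on arm, visit (categorical), arm × visit and baseline T-TRiPS × visit; or
- a T1-T3 mixed model with arm means constrained equal at T1.

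Limit the between-arm tests under Descriptive Analysis to T2 and T3, and show T1 descriptively. Further covariates such as role or years in the field are not part of this change, since nothing in the document shows that they predict the score.

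The cost is about two sentences of SAP text and, if the model used was different, one re-run on existing data. The document is dated 28 July 2022 and cites results already published, so any re-run should be labelled post hoc and shown beside the reported analysis.

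### Unequal variance triggers a switch to Kruskal-Wallis in the per-wave T-TRiPS comparison, which does not repair it; Welch's test at every wave would, at no material cost (minor)

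*Combined protocol and SAP*

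**What the plan says.** The rule is in the SAP under Descriptive Analysis. Its purpose is stated as "To compare the raw outcome differences between conditions at each time point". For the continuous outcome the default is 1-way ANOVA, and the alternative is the "Kruskal-Wallis H test (if variance is not equal between conditions"). The significance level is .05. Unequal variance is the only stated trigger; non-normality is not mentioned. No variance test or threshold is named.

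Three other places bear on it:
- Outcome measures gives the score to be analysed: "Theta standardized scores will be obtained for the analysis".
- Power describes "a linear mixed model examining the impact of intervention relative to control, including an interaction with time", sized "to detect a difference of 0.75 between the intervention and control conditions on the T-TRiPS". That target is a difference in means.
- Methods describes simple 1:1 randomization, so arm sizes are equal only in expectation, and reports 563 recruited.

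**The concern.** The rule answers a problem with a test that does not address it. Kruskal-Wallis takes its null distribution from the assumption that both arms have the same distribution. Unequal spread breaks that assumption, so the rule selects the test in the situation where it stops being, in general, a test of equal means.

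Two mechanisms follow.
- **Symmetric scores with a common centre.** A random score from one arm is still equally likely to fall above or below one from the other. Only the variance of the rank sum is misjudged, and the effect is small.
- **Skewed scores with equal means but different spreads.** That probability moves away from one half. Kruskal-Wallis then detects a real difference in ranks that is not a difference in means, and does so more often as the sample grows.

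The switch is also decided wave by wave, so one follow-up could be tested on means and the other on ranks. At stake is how to read the P values for the raw primary-outcome comparisons at 1 week and 3 months against a target expressed as a mean difference.

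**Working it through.** **Inputs from the documents.** Difference 0.75, SD 1.82 (one value, not by arm), 103 per arm at the end, retention 75% then 85%, 324 planned and 563 recruited, alpha .05.

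**Assumptions, because the documents are silent.** Two-sided tests; a Brown-Forsythe (median-centred Levene) gate at .05; SD ratio between arms, mainly 1.4; normal scores, or gamma scores with skewness 0.5 or 1; the planned retention applied to the 563 recruited.

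**The plan's own figure.** No operating figure is stated for this rule. The only related figure is 80% power with 206 participants.
- Plain two-sample comparison, n per arm: 2 × (1.960 + 0.842)² × 1.82² / 0.75² = 92.4, so 93 per arm.
- At 103 per arm: 0.75 / (1.82 × √(2/103)) = 2.957; Φ(2.957 − 1.960) = 84.1% (83.7% by the t distribution).
- The stated 80% is therefore not reproduced exactly. The plan is on the conservative side, the tested contrast is not specified, and this has no bearing on the present point.
- Retention: 324 × 0.75 = 243 (stated 242); × 0.85 = 206.6, which agrees with 206.

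**Arm sizes used.**
- Planned: 103 per arm. The 95% range under simple randomization of 206 is 103 ± 1.96 × √(206/4) = 89 to 117.
- From 563: 563 × 0.75 / 2 = 211 per arm at 1 week; × 0.85 = 179 per arm at 3 months. The matching 95% range at 1 week is 211 ± 1.96 × √(422/4) = 191 to 231.

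**Type I error for the mean (means equal, SD ratio 1.4).** Rule = ANOVA, or Kruskal-Wallis if the gate gives P < .05. Each setting had 10,000 to 20,000 simulated trials; at 20,000 the standard error is √(0.05 × 0.95 / 20,000), about 0.15 points. A range is shown where repeat runs differed.

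| Scores | Arms | Rule | Welch |
|---|---|---|---|
| Normal | 103/103 | 5.4% | 5.1% |
| Normal, wider spread in smaller arm | 89/117 | 5.6–6.0% | 5.0–5.3% |
| Normal, wider spread in larger arm | 117/89 | 4.6% | about 5% |
| Normal, wider spread in smaller arm | 191/231 | 5.3–5.7% | 4.9% |
| Gamma, skew 0.5 | 103/103 | 5.7–6.1% | 4.9–5.2% |
| Gamma, skew 0.5 | 211/211 | 7.2–7.3% | 4.9–5.1% |
| Gamma, skew 1 | 103/103 | 7.5–7.7% | 5.0–5.1% |
| Gamma, skew 1 | 179/179 | 12.0–12.5% | 4.9% |
| Gamma, skew 1 | 211/211 | 14.0–14.2% | 4.9–5.0% |

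In the last row plain ANOVA gives 4.9%, so with equal arms and skewed scores switching does worse than not switching. Simulated Rasch theta scores (26 items, latent SD ratio 1.2 to 1.4, latent skew 0 or 1; 4,000 runs, error about 0.7 points) gave 4.0 to 7.3% for the rule and 4.3 to 5.7% for Welch.

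**Power (difference 0.75, 103 per arm, normal scores).**
- Equal SDs of 1.82: Welch 83.4–83.7%, rule 83.2–83.6%.
- SD ratio 1.4: Welch 67.4–67.5%, rule 65.1–65.5%.

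**The case against.** The case for leaving the rule alone has several parts.

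- **It is descriptive.** The heading and the stated purpose say so, and the Power section names a linear mixed model. This stands and sets the severity. The mixed model does appear only in the Power section, however, and the per-wave tests carry a .05 significance level on the primary outcome.
- **Kruskal-Wallis is valid under a strict null.** If the intervention changes nothing and dropout does not differ between arms, the arms share one distribution at every wave. This stands for baseline and, on those conditions, for both follow-ups. Every inflated figure above needs spreads to differ while means stay equal.
- **With normal scores and unequal arms, Kruskal-Wallis is closer to 5% than ANOVA.** True: at 137/69 with SD ratio 2 and the wider spread in the smaller arm, it gives 8.9% against 11.5% for ANOVA. Welch gives 5.1%. An imbalance that large is beyond chance and would need differential dropout.
- **The large errors need skew.** True, and the documents report none.

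A reader might infer that a switched wave must go without an effect estimate. The documents do not support that: means can be reported whichever test supplies the P value, and the SAP does not describe reporting format. A reader might also infer that choosing different tests at 1 week and 3 months often changes the conclusion. With normal scores, equal means and 103 per arm, the rule and Welch give the same .05 decision in 98.1 to 99.9% of runs.

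**Conclusion.** The point holds as a minor one. The stated response to unequal variance is the wrong tool for comparing means, and a better one is available at no material cost. With symmetric scores and chance-level arm imbalance the distortion is small: about 5 to 6% when the smaller arm has the wider spread, and slightly below 5% in the reverse case. Within chance-level imbalance it becomes material only if scores are also skewed. At SD ratio 1.4 that means about 7% at skew 0.5 with 211 per arm, and about 8% (103 per arm) to 14% (211 per arm) at skew 1.

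These are ranges under an assumed gate, assumed SD ratios and assumed skew, not predictions for this trial. The documents do not support reading them as evidence that the trial's main result is wrong: they do not say whether any wave was switched, and the main inference need not rest on these comparisons.

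**What to change.** Replace the ANOVA/Kruskal-Wallis rule with Welch's unequal-variance t-test for every raw per-wave T-TRiPS comparison, with no variance pre-test, reported as a mean difference with 95% CI. Keep any rank test as a labelled sensitivity analysis. Because the text says the tests were already used, state whether any wave was switched to Kruskal-Wallis and, if one was, re-report it with Welch.

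The cost is one sentence and at most three re-run comparisons on existing data, with no change to the sample size.
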